CLINICAL STUDY PROTOCOL

Observational Study of Individual or Group Template

Investigating the Impact of a Shared Decision-Making Tool on Patient Attitudes and Behaviors Regarding Treatment for Knee Osteoarthritis

2000032637

Protocol Version

February 18, 2022

Version 1

Confidentiality Statement:

Synopsis

Purpose

The purpose of this study is to determine the impact of a Shared Decision-Making Tool (SDMT), which provides information about osteoarthritis disease progression, on a patient's decision to pursue treatment for knee osteoarthritis.

Primary Objective

The primary objective of this study is to assess the impact of the shared decision-making tool on a patient's decision to seek treatment for knee osteoarthritis.

Secondary Objective

Our secondary objectives include investigating the impact of the SDMT on patient understanding of disease progression as well as patient understanding of the impact of treatment on disease progression. Additional secondary objectives include evaluating the impact of the SDMT on patient behaviors and engagement with treatment modalities.

Study Design

This is a randomized control trial in which participants will be assigned to one of two arms. Patients in the control arm of the study will watch a short video and then receive standard of care counseling with an orthopaedic surgeon. Patients in the treatment arm of the study will watch a short video and then receive standard of care counseling with an orthopaedic surgeon that includes discussion of the SDMT. All patients will complete pre- and post-visit surveys designed to measure the severity of their knee osteoarthritis and their willingness to proceed with different treatment modalities.

All patients who are receiving care for knee osteoarthritis with one of the participating orthopaedic surgeons, and are greater than age 18 and speak English, will be eligible for inclusion in the study. The study will be conducted at Yale-affiliated clinics.

Study Date Range and Duration

Patient responses for this study will be collected between May 23rd, 2022– August 08th, 2022.

Number of Study Sites

- Yale Ortho – New Haven Office
Yale Physician Building [name]
- Yale Ortho – Milford
[name]
- Yale Medicine Multispecialty
[name]

Primary Outcome Variables

The variables used to measure the primary outcome will include patient willingness to proceed with specific treatment modalities as measured by the pre- and post-visit surveys.

Secondary and Exploratory Outcome Variables (if applicable)

The variables used to measure the secondary outcomes will include patient understanding of disease progression, patient understanding of the impact of treatment modalities on disease progression, patient-reported pain and functional status, and patient engagement in treatment modalities as measured by the pre- and post-visit surveys.

Study Population

The target population for this study will be persons aged 45-65, who have mild to moderate knee pain, and are seeking care from an orthopaedic surgeon specializing in total knee arthroplasty.

Number of Participants

We are seeking 200 participants. The attrition rate is assumed to be 10-20%. It may be lower due to the short follow-up period of one month, or higher given the targeted patient demographic. We anticipate enrolling 200-250 patients to account for loss to follow-up.

Study Schedule

We anticipate at least an initial patient visit that would take 30-50 minutes including an explanation of the study and obtaining consent, pre-study survey, PROMIS survey, clinical exam, Shared Decision-Making Tool discussion, and any additional questions the patient may have.

Protocol Revision History

Include the IRB approved protocol version number and date for each revision of the protocol. All version history should remain in the table and never be deleted. The oldest IRB approved version of the protocol should be listed on the top row. The most recent IRB approved version should be listed on the bottom row.

Version Date	Summary of Substantial Changes

Statement of Compliance

This document is a protocol for a human research study. The purpose of this protocol is to ensure that this study is to be conducted according to the Common Rule at 45CFR46 (human subjects) and other applicable government regulations and Institutional research policies and procedures.

Abbreviations

Abbreviation	Explanation
OA	Osteoarthritis
PI	Principal Investigator
SDMT	Shared Decision-Making Tool
UPIRSO	Unanticipated Problems Involving Risks to Subjects or Others

Glossary of Terms

Glossary	Explanation
----------	-------------

Table of Contents

Preface	2
Synopsis	3
Purpose	3
Primary Objective	3
Secondary Objective	3
Study Design	3
Study Date Range and Duration	4
Number of Study Sites	4

1.1 Background

Knee osteoarthritis (OA) is the most commonly diagnosed type of arthritis, with approximately thirteen percent of women and ten percent of men over age sixty suffering from symptomatic knee osteoarthritis. While the character and intensity of osteoarthritis (OA) symptoms is different for each patient, OA is generally a progressive disease that can result in disability, loss of function, and ultimate loss of quality of life for patients (Hsu & Siwiec, 2021). While OA has no cure, management of this condition centers around severity of symptoms and current disease progression, with common treatment modalities including exercise, weight loss, and patient education, with additional interventions such as non-steroidal anti-inflammatory drugs and intraarticular injections (Katz et al., 2021). Pursuing these non-operative interventions can lengthen the time a patient with osteoarthritis (OA) has before surgery, such as total joint replacement, becomes the primary option.

Utilizing shared decision-making (SDM) can facilitate conversations that can benefit patients before OA becomes a major health concern. SDM in the clinic relies on three principles: 1) having the clinician provide unbiased and accurate medical advice on all treatment alternatives, including the possibility of not receiving treatment; 2) having the clinician communicate these options to the patient; and 3) having the clinician respect and prioritize the patient's values and preferences based on the discussed information, goals of treatment, and future concerns and possible treatment burdens (Johnson, 2021). Therefore, building provider-patient communication tools that resonate with all stakeholders is necessary to inform patients as they work to make health decisions reflective of their individual beliefs.

Previous attempts to address these clinical concerns resulted in the development of the [Shared Decision-Making Tool](#) (SDMT), which was designed to provide a personalized, patient-centered framework for clinical discussions regarding treatment options for knee OA. The tool functions through patient input of information such as pain severity and current symptoms, alongside other demographic information such as age, race, and comorbidities, to offer a series of outcomes to better illustrate how the patient's specific disease presentation will progress (Johnson, 2021). Ultimately, using the SDMT may impact patient behavior if patients change their treatment preferences after utilizing the tool. This can empower them to seek additional support over time and maintain communication with their orthopedist to ensure they are on a healthier path.

In addition to the patient's efforts, the SDMT can address provider influences. Bias likely influences patients; experiences with clinicians, and the SDMT can serve to deter implicit bias by focusing on the disease of patients, thus avoiding the development of healthcare disparities (Marcelin et al., 2019). Encouraging individuals who have historically not taken advantage of preventive care or healthy lifestyles to induce change is paramount to making the medical experience in America more equal for all its citizens and reducing total societal costs.

This study seeks to determine if providing an overview of future disease progression through the SDMT helps patients, with a focus on the following concerns: i) whether it assists the patient with readiness for treatment; ii) whether the patient finds the overview and information helpful immediately and/or one month after the discussion; and iii) whether patients consider the mid- to long-term consequences of treatment options.

To address these concerns, we have designed a prospective study to observe the use of a SDMT and its impact on a patient's decision to pursue treatment options recommended by their provider.

Johnson C. B. (2021). A Personalized Shared Decision-Making Tool for Osteoarthritis Management of the Knee. *Orthopedic nursing*, 40(2), 64–70. <https://doi.org/10.1097/NOR.0000000000000739>

1.2 Prior Experience (if applicable)

2 Rationale/Significance

2.1 Rationale and Study Significance

Research on the Shared Decision-Making (SDMT) is instrumental to determine if it is effective at motivating patients to pursue treatment options that can subsequently improve mobility and their quality of life.

2.2 Purpose of Study/Potential Impact

The main purpose of this study is to determine the impact of the SDMT on patient decision-making regarding various treatment modalities for knee OA. If the SDMT is found to be beneficial, it can be implemented to help engage patients in their care and support more efficient implementation of treatment suggestions. This subsequently will improve patient's quality of life. Getting patients who have not taken advantage of preventive care or healthy lifestyles to change is paramount to making the medical experience in America more equal for all its citizens and reducing total societal costs. Building provider-patient communication tools that resonate with all stakeholders should inform patients as they work to make health decisions that reflect their individual beliefs.

To determine whether this information helps patients, we have designed a prospective, randomized controlled implementation study outlined here.

2.3 Potential Risks and Benefits

2.3.1 Potential Risks

Participation in this research involves the potential risk of breach in confidentiality to the patient's stored health information.

2.3.2 Potential Benefits

The study provides patients with additional information about knee pain and osteoarthritis. The knowledge gained will help target helpful information for patients. The study can support providing an information tool used by patients to better understand the role of lifestyle and treatment on their prognosis.

3 Study Purpose and Objectives

3.1 Hypothesis

We hypothesize that patients who are exposed to the SDMT will have an increased willingness to pursue treatment modalities for OA.

3.2 Primary Objective

The primary objective of this study is to assess the impact of the shared decision-making tool on a patient's decision to seek treatment for knee osteoarthritis.

3.3 Secondary Objective (if applicable)

Our secondary objectives include investigating the impact of the SDMT on patient understanding of disease progression and patient understanding of the impact of treatment on disease progression. Additional secondary objectives include evaluating the impact of the SDMT on patient behaviors and engagement with treatment modalities.

4 Study Design

4.1.1 General Design Description

This is a randomized control trial in which participants will be assigned to one of two arms. Patients in the control arm of the study will watch a short video and then receive standard of care counseling with an orthopaedic surgeon. Patients in the treatment arm of the study will watch a short video and then receive standard of care counseling with an orthopaedic surgeon that includes discussion of the SDMT. All patients will complete pre- and post-visit surveys designed to measure the severity of their knee osteoarthritis and their willingness to proceed with different treatment modalities.

All patients who are receiving care for knee osteoarthritis with one of the participating orthopaedic surgeons, and are greater than age 18 and speak English, will be eligible for inclusion in the study. The study will be conducted at Yale-affiliated clinics.

4.1.2 Study Date Range and Duration

Patient responses for this study will be collected between May 23rd, 2022 – August 8th 2022.

4.2 Outcome Variables

4.2.1 Primary Outcome Variables

The variables used to measure the primary outcome will include patient willingness to proceed with specific treatment modalities as measured by the pre- and post-surveys.

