5.1 Study Procedures

Potential subjects will be identified by the PI and participating orthopaedic surgeons. The PI and Sub-I will recruit potential subjects for this study.

Subjects will be consented in a private room by a designated member of the study team. Each subject will be consented in the language appropriate and presented with a consent form, written in that language. All aspects of the study will be discussed with the potential subject including the reason the subject is being asked to participate, the schedule of visits, the study activities that will occur, and the risks and benefits of participation. The subject will then have an opportunity to ask any questions they have. Once all questions have been answered and the subject feels that he/she would like to participate, the designated member of the research team will obtain verbal consent for the study.

A subject's capacity to provide consent will be evaluated by a member of the consenting staff based on the questions the subject asks about his/her involvement in the study as well as by asking the subject questions pertaining to aspects of the study.

Eligible patients who agree to participate and provide verbal informed consent, will be randomized to participate in either the Control Group or Intervention Group. Both groups will complete the PROMIS Computer Adaptive Test and pre-survey as well as watch a short video providing general information about knee OA. The intervention for the intervention group will be the surgeon utilizing the SDMT during the visit. Both the control and intervention group will complete the post-event survey immediately after completing the control or intervention and then 1 month later.

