5.4 Statistical Method

5.4.1 Statistical Design

Power Analysis

Statistical Power is determined by the estimated mean and standard deviation of one primary endpoint or composite endpoint to determine ending sample size in each group (test and control). The study power varies with Standard Deviation and Expected Difference in Performance between control and investigational groups. The power is the probability the study will detect a statistical difference between the two groups based on the expected standard deviation and mean difference between the two groups.

This study for which a power of 0.8 is sufficient and we expect a difference in score between the test group and control group to be at least 20% and a standard deviation of 10 points or less. Even if the difference between groups drops to 10% with a standard deviation of 10 points our target sample size of 200 patients is sufficiently powered.

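### The plan gives two conflicting primary outcomes (willingness on the pre/post surveys, and an undescribed SDM Tool item in Table 2) and fixes no single willingness score or primary model

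*Combined protocol and SAP*

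**What the plan says.** Four places point to willingness:

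- Section 4.2.1 says the primary outcome variables will include "patient willingness to proceed with specific treatment modalities as measured by the pre- and post-surveys".
- The synopsis says the same: "patient willingness to proceed with specific treatment modalities as measured by the pre- and post-visit surveys".
- The hypothesis in 3.1 is that patients exposed to the tool will show "increased willingness to pursue treatment modalities for OA".
- Section 5.4.3 plans univariate and multivariate regressions of willingness on the SDMT.

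Section 4.1.1 says all patients complete "pre- and post-visit surveys designed to measure the severity of their knee osteoarthritis and their willingness to proceed with different treatment modalities".

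Table 2 in section 5.4.2 points elsewhere. It has five rows: the pre-appointment survey, PROMIS, and three numbered outcome surveys. Item 1, SDM Tool, carries the table's only primary-outcome label. Item 2 is the post-appointment survey, described as identical to the pre-survey, with no primary or secondary label. Item 3, the one-month survey, is labelled secondary. The text above the table calls item 1 the SDM Survey and says each line item of the three surveys is scored 1 to 5. The pre-appointment survey is scored as yes/no or in categories.

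Section 5.1 lists what patients complete: "Both groups will complete the PROMIS Computer Adaptive Test and pre-survey as well as watch a short video", and then "Both the control and intervention group will complete the post-event survey immediately after completing the control or intervention and then 1 month later". No SDM Survey appears there. In that section the SDMT is the intervention, used by the surgeon in one arm.

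Section 5.4.1 bases power on the "estimated mean and standard deviation of one primary endpoint or composite endpoint" without choosing between them. It expects a difference of at least 20% with an SD of at most 10 points, and adds a fallback: "Even if the difference between groups drops to 10% with a standard deviation of 10 points", for which 200 patients are said to be enough.

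**The concern.** The primary outcome decides what the trial can claim. An analyst working from 4.2.1 would compare willingness between arms; one working from Table 2 would analyse item 1. If item 1 is tied to use of the tool, control patients may have no data on it. Nothing in the text rules that out.

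Settling on willingness does not finish the job. Several modalities, several items per survey, two post-visit assessments and two kinds of regression leave many candidate results. No combining rule, primary model or multiplicity control is stated. The power statement then refers to a score that has not been named, so it cannot be verified.

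**Working it through.** **1. The two definitions side by side**

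| Question | Synopsis, 3.1, 4.2.1, 5.4.3 | Table 2, item 1 |
|---|---|---|
| Construct | Willingness to proceed with modalities | Not described |
| Instrument | Pre- and post-surveys | SDM Tool / SDM Survey, listed apart from those surveys |
| Given to both arms? | Yes (4.1.1, 5.1) | Not stated; absent from 5.1 |
| Timing | Visit day and one month; primary one not named | Not stated |

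The secondary label on the one-month survey implies that the visit-day assessment is primary, but no section says so.

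**2. Is a change score defined?** The baseline survey is scored yes/no or in categories and the post-survey 1 to 5. Without a mapping between the two, a simple pre-to-post difference is undefined.

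**3. Can an SD of 10 points belong to the stated scale?** The largest SD on a 1-5 scale is half the range: (5 − 1)/2 = 2. The same bound holds for a mean of such items. A sum of k items has maximum SD 2k, so an SD of 10 needs k of at least 5. A summed or rescaled composite could fit, but none is named.

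**4. The plan's own power claim.** Alpha, sidedness and allocation are not stated; I assume two-sided 0.05 and 1:1, so 100 per arm. By the normal approximation, power = Φ(d·√(n/2) − 1.96), with d = difference/SD and √(100/2) = 7.07.

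- If 10% means 10 points on a 0-100 score with SD 10, then d = 1.0 and power = Φ(7.07 − 1.96) = Φ(5.11), above 99.9%. Only 16 per arm would give 80%. The claim is true on this reading, but 200 does not derive from these inputs.
- If 10% is relative to an assumed mean of 50 (5 points), d = 0.5: power 94%.
- If it is relative to an assumed mean of 30 (3 points), d = 0.3: power 56%, with 175 per arm needed for 80%.

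**5. The same 10% on a 1-5 item or item mean.** Ten percent of the range is 0.10 × 4 = 0.4 points. The SDs are assumptions.

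| SD | d | Power, normal approx. | Power, t test | Per arm for 80% (t test) |
|---|---|---|---|---|
| 0.8 | 0.50 | 94.2% | 94.0% | 64 |
| 1.0 | 0.40 | 80.7% | 80.4% | 100 |
| 1.2 | 0.33 | 65.4% | 65.0% | 143 |

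Baseline adjustment is not counted and would raise these figures.

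**6. False-positive chance if each modality is tested.** The number of modalities is not given; 3 and 6 are illustrative. One time point, two-sided 0.05 each. Independent tests: 1 − 0.95^k. Correlated tests: simulation of equicorrelated normal statistics, 1,000,000 draws.

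| Correlation | 3 modalities | 6 modalities |
|---|---|---|
| 0 | 14.3% | 26.5% |
| 0.5 | 12.6% | 20.8% |
| 0.8 | 9.9% | 13.8% |

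One prespecified test gives 5%.

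**The case against.** Most of the protocol points to willingness. The outlier is one comment cell in a table under a sample-size heading, which may be a label slip, or item 1 may itself hold the willingness items. The survey forms and the figure at the start of section 5 were not available for this review, and they might describe item 1. Both readings are possible, but the reader should not have to choose between them: the conflicting statements are both in the current text, and the table separates item 1 from the surveys that 4.2.1 cites.

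The power illustration uses the fallback effect, not the expected one. At 20% of the 1-5 range (0.8 points), 100 per arm gives power above 99.9% at SDs of 0.8 and 1.0, 99.7% at 1.2, and about 80% even at SD 2.0. That is correct, and the expected effect is well covered on that scale. But 5.4.1 also claims adequacy for the 10% case, and that claim depends on the score.

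The modality counts and correlations are assumed, and the plan does not say each modality is tested. This stands, so the 10% to 26% range shows what the open wording permits and does not estimate what will happen. Categorical baseline scoring could also mean five ordered categories matching the post-survey, but the plan does not say so.

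**Conclusion.** The concern holds and must be fixed before analysis. The plan contradicts itself on the primary outcome, and its willingness definition does not determine one score, one stated time point or one model. This part rests on the text alone and needs no assumption. The hypothesis remains testable, because willingness data should exist in both arms.

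The numerical consequences are conditional. For the plan's 10% case, power at 200 patients runs from above 99.9% (0-100 score, SD 10) down to 65% (1-5 item or item mean, assumed SD 1.2), assuming 1:1 allocation and two-sided 0.05. Unadjusted testing of 3 to 6 modalities would put the false-positive chance at about 10% to 26% instead of 5%.

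**What to change.** 1. In 5.4.2, state what item 1 is: its content, when it is completed and by whom. If it is not the instrument carrying the willingness items in both arms, move the primary label in Table 2 to the immediate post-appointment survey. If it is, say so, name it in the synopsis and 4.2.1, and add it to 5.1 for both arms.
2. In either case, prespecify one willingness score at the visit-day assessment: a named item, or a composite with its modalities listed, its combining rule, and a statement of whether surgery counts.
3. In 5.4.3, compare that score between arms as randomised, in one stated regression at two-sided 0.05, adjusted for the baseline willingness response. Entering baseline as categories avoids the need for a change score.
4. Make single-modality and one-month results secondary, with multiplicity control across modalities (Holm, for example).
5. In 5.4.1, restate the expected difference and SD on the chosen score's scale and report the resulting power at 200 patients.

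The cost is wording in the synopsis, 4.2.1, 5.1, 5.4.1, 5.4.2 and 5.4.3. There are two real downsides: modality-specific claims become secondary, and the restated power may be less favourable than the plan now says.
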